5.4.6 Definitions and Terminology

Study Day

Study day will be defined as Event Date – Study Day 1 + 1

Study Day 1

Day 1 is defined as the date of first dose of eteplirsen at the Week 1 visit during the 4658-204 Study.

Days on Study

Days on Study is the number of days from Study Day 1 to the date of study completion or early termination as recorded on the END OF STUDY VISIT CRF.

Days on Study Drug

Days on Study Drug is the number of days from the date of first dose to the date of the last dose of the specific study medication as recorded on the STUDY DRUG ADMINISTRATION CRF.

Planned Number of Infusions

The planned number of infusions will be based on the subject's last local site visit. The subject will be expected to receive an infusion once weekly up until their last local site

visit. If a subjects completes 100 local site visits and then completes or discontinues the study the planned number of infusions will be 100.

Treatment Group

All subjects received 30 mg/kg weekly of eteplirsen and will be analyzed in the same group.

Time Since DMD Diagnosis

The time since DMD diagnosis, in months, will be calculated as Month and Year of first dose – Month and Year of diagnosis

Treatment-Emergent Adverse Event

An AE is considered treatment-emergent if it occurs on or after the initiation of the first dose of eteplirsen and within 28 days of last dose.

Treatment Related Adverse Event

A treatment-related AE is any adverse event reported on the CRF that is marked as definitely, probably or possibly related to study drug. Additionally, it is assumed that an AE without a relationship is treatment-related.

Treatment-Emergent Laboratory Abnormality

[figure not shown]
A treatment-emergent laboratory abnormality is defined as any laboratory abnormality (as defined in section 5.5.7.2) that occurs following the initiation of eteplirsen which was not present at Baseline.

Prior Medication

A prior medication is any medication taken prior to the first study drug administration.

Concomitant Medication

A concomitant medication is any medication that is taken on or after the first study drug administration.

Final Analyses

An analysis will be performed once all subjects complete their End of Study visit and the resulting clinical database has been cleaned, quality checked and locked through the data cut.

5.4.8 Programming Conventions

This section details general conventions to be used for the statistical analyses. Departures from these general conventions will be specified in appropriate sections.

- Summary statistics will consist of the number and percentage of responses in each level for categorical variables, and the sample size (n), mean, median, standard deviation (SD) or as appropriate the standard error of the mean (SE), minimum, and maximum values for continuous variables.
- All mean and median values will be formatted to a precision of 1 more decimal place than the measured value on the electronic case report form (eCRF). Standard deviation (SD) and SE values will be formatted to a precision of 2 more decimal places than the measured value on the eCRF. Minimum and maximum values will be presented with the same precision as the measured value on the eCRF. Percentages will be presented to a precision of 1 decimal place.
- The number and percentage of responses will be presented in the form XX (XX), where the percentage is in the parentheses. Unless otherwise specified, the

denominator for percentages will be the number of subjects in a given treatment group within the analysis population of interest.

- Study day will appear in the data listings as appropriate.
- Date variables will be formatted as DDMMYYYY for presentation. In the case of missing day, month, and/or year information, "UN" will be presented. For example, a date with a missing month and day will be presented as UNUNYYYY.
- Adverse events (AEs) with missing relationship or severity will be presented as "Related" or "Severe", respectively. However, missing values will be presented in the data listings as missing.
- Tables, figures, and listings will be presented in landscape orientation.
- P-values will be reported as two-sided p-values. If a p-value is less than 0.001 it will be reported as <0.001.
- SAS® Version 9.2 or higher will be the statistical software package used for all data analysis.

[figure not shown]
5.5. Statistical Analyses

5.5.1 Subject Disposition

Subject disposition will be summarized with frequency count and percentage for the following items: subjects who received the study medication (safety population), subjects who completed the study through 96 weeks, and subjects who discontinued early. The reasons for discontinuation will be summarized for all enrolled subjects.

Subject disposition and subject eligibility (including inclusion/exclusion criteria) will be presented in data listings.

5.5.1 Demographics and Baseline Characteristics

5.5.2 Prior and Concomitant Medications

Concomitant medications will be summarized by displaying the number and percentage of subjects with each drug classification and preferred term. All medications, whether prior or concomitant, will appear in the data listings.

5.5.3 Medical History

Medical history data will be presented in the data listings.

5.5.4 Protocol Deviations

A listing and summary of protocol deviations will be provided.

5.5.5 Dosing

The cumulative exposure (mg), total volume of drug administered (mL), total number of infusions received, total number of infusions planned and compliance (calculated as 100*number of infusions received/number of infusions planned) will be summarized. Dosing information will be provided in a data listing.

5.5.6 Efficacy

5.5.7 Safety

Safety analyses will be descriptive in nature.

5.5.7.1. Adverse Events

Adverse events will be mapped to MedDRA v17.1 preferred terms (PT) and system organ classifications (SOC). Multiple occurrences of the same AE (at the PT level) in the same subject will be counted only once in the frequency tables. All adverse event tables will be summarized by Baseline ambulatory status and overall. If a subject experiences multiple episodes of the same event with a different relationship/severity, the event with the strongest relationship or maximum severity to the study drug will be used to summarize the AEs by relationship and severity.

Only treatment-emergent adverse events (TEAEs) will be summarized. Non-emergent events will be included in the subject listings. TEAEs and treatment-related TEAEs will be summarized by SOC, PT, and severity. Additionally, serious AEs (SAEs), regardless of their treatment-emergent status, will be summarized by SOC and PT. The following listings will be produced:

- 1) All AEs
- 2) Moderate and Severe AEs
- 3) Treatment-Related AEs
- 4) SAEs

5) AEs leading to discontinuation

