13.8.2.1. Adverse Events

Only treatment-emergent adverse events (TEAEs) will be summarized. Non-emergent events will be recorded in data listings. For all AE tables, the number and percent of patients reporting AEs (grouped by the Medical Dictionary for Regulatory Activities [MedDRA] System Organ Class [SOC] and Preferred Term [PT]) will be summarized by treatment condition. In general, tables will have events categorized into all TEAEs and treatment-related TEAEs.

Multiple occurrences of the same AE (at the PT level) in the same patient will be counted only once in frequency tables. If a patient experiences multiple episodes of the same event with different relationship/severity, the event with the strongest relationship and maximum severity to

IP will be used to summarize AEs by relationship and severity. Treatment-related TEAEs will be defined as those that the Investigator considers possibly/probably or definitely related to the IP.

The following summary tables will be produced:

- TEAEs
- TEAEs by severity
- Treatment-related TEAEs
- Treatment-related TEAEs by severity
- SAEs

In addition, all SAEs, regardless of their treatment-emergent status will be summarized by SOC and PT.

The following listings will be produced:

- Non-treatment emergent AEs
- All TEAEs
- AEs leading to discontinuation
- SAEs

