5. STATISTICAL METHODS

5.1. Sample Size

There is no formal sample size calculation. The sample size is based on qualitative considerations and is sufficient to provide safety evaluation of eteplirsen in the studied population. Approximately 20 patients will be enrolled in this study.

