5.5.7.2. Laboratory Measurements

Descriptive statistics for continuous hematology, clinical chemistry, urinalysis, and coagulation laboratory measurements will be presented by time point. Summary statistics for each lab parameter and time point as well as the change from Baseline to the time point will be displayed. For each numeric laboratory parameter, box plots of values over time will be generated. A shift table will compare N (%) of low, normal, and high status of the lab values at Baseline to their worst value post-Baseline through Week 96. A table summarizing the frequency and percent of subjects meeting the predefined markedly abnormal criteria at each visit will be presented. The predefined markedly abnormal criteria are defined below in Tables 3-1, 3-2, and 3-3. All laboratory values will be displayed in a data listing.

Table 3-1 Predefined Markedly Abnormal Hematology Laboratory Values

Test	Unit	Markedly Abnormal Criteria
Hematocrit	1	< LLN
Hemoglobin	g/L (or mmol/L)	< LLN
Red blood cell count	T/L	< LLN
White blood cell count	count/L	$>1.5 \times ULN \text{ or } < LLN$
Platelet count	10^3/L	< 150 or < 200 with a decrease of at least 100
Basophils (abs)	count/L	> ULN or < LLN
Eosinophils (abs)	count/L	> 1.5xULN or < LLN
Lymphocytes (abs)	count/L	< LLN
Monocytes (abs)	count/L	< LLN
Neutrophils (abs)	count/L	>1.5 × ULN or < 1000

ULN = upper limit of normal

LLN = lower limit of normal

abs = absolute

Table 3-2 Predefined Markedly Abnormal Chemistry Laboratory Values

		Predefined	Change	
Test	Unit	Decrease	Increase	Markedly Abnormal Criteria
Fasting blood glucose*	mmol/L	3.1	3.2	
Urea (BUN)	mmol/L			Value >1.5 × Baseline Value AND > ULN
Creatinine	μmol/L		35	Value >1.5 × ULN
Sodium	mmol/L	8	8	
Potassium	mmol/L	1.1	1.0	Value >5.5 mmol/L or < 3 mmol/L
Chloride	mmol/L	9	8	
Uric acid	μmol/L			>1 × ULN
Calcium#	mmol/L	0.30	0.30	
Total cholesterol	mmol/L		1.73	
AST (SGOT)	U/L			Value ≥3 × Baseline Value
ALT (SGPT)	U/L			Value ≥2 × Baseline Value
Gamma GT (GGT)	U/L			Value >3 × Baseline Value OR > ULN
Alkaline phosphatase	U/L			Value >1.5 × ULN
Total protein@	g/L	11	10	
Albumin	g/dL	1 g/dL decrease or	1 g/dL increase	Value < LLN or > ULN
Total bilirubin ^{&}	μmol/L		10	Value >1.5 × ULN
LDH	U/L			Value ≥2 × Baseline Value
Creatine phosphokinase	U/L			Value ≥2 × Baseline Value
Triglycerides	mmol/L	_	2.88	
Cystatin C	mg/L			>ULN

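### AE tables give crude patient percentages with no common time at risk (early exit to about 148 weeks); a Week 96 display and exposure-adjusted rates are needed

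*SAP*

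**What the plan says.** **Measure.** Protocol 13.8.2.1 sets the form of the tables: "For all AE tables, the number and percent of patients reporting AEs". SAP 5.5.7.1 adds that "Multiple occurrences of the same AE (at the PT level) in the same subject will be counted only once in the frequency tables". Unless otherwise specified, SAP 5.4.8 makes the "denominator for percentages will be the number of subjects in a given treatment group within the analysis population of interest".

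**Split.** SAP 5.5.7.1: "All adverse event tables will be summarized by Baseline ambulatory status and overall".

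**Window.** SAP 5.4.6 calls an event "treatment-emergent if it occurs on or after the initiation of the first dose of eteplirsen and within 28 days of last dose". There is no cut at Week 96. The final analysis follows all End of Study visits, so events in the extension are included.

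**Follow-up.** SAP 1 gives 96 weeks of weekly dosing, then an extension of at most 48 weeks. Under Protocol 7.1 the extension runs until commercial availability or transfer to another eteplirsen study. Protocol 8.5 lets a patient withdraw at any time.

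**Contrast.** The laboratory shift table in SAP 5.5.7.2 uses the "worst value post-Baseline through Week 96", and the ECG shift table in SAP 5.5.7.4 has the same limit.

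**Exposure.** SAP 4.4.1 calculates days from first to last dose for each subject. SAP 5.5.5 summarizes amount, volume, infusions and compliance. Neither is stated by ambulatory status or used as an AE denominator.

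**Size.** SAP 5.1: "Approximately 20 patients will be enrolled in this study" and "There is no formal sample size calculation".

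**The concern.** A percentage of patients with at least one event rises with the time they are watched. When that time varies between patients and is not stated, the reader cannot say what period the percentage refers to. Safety is the study's primary objective and AE incidence is the first safety endpoint listed in Protocol 7.3.1, so this is the figure most readers will take away.

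Two features sharpen the problem. First, every AE table appears in columns by Baseline ambulatory status, which invites a side-by-side reading. If one group stays longer in the extension, or leaves earlier, its percentages move for that reason alone. Second, the AE tables run to the end of each patient's follow-up while the lab and ECG shift tables end at Week 96, so safety displays in one report cover different periods.

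**Working it through.** The plan states no AE rate, power or expected incidence, so there is no figure of its own to reproduce. The check covers the time at risk and what unequal time does to a crude percentage.

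**1. Longest window.** Dosing: 96 + 48 = 144 weeks (SAP 1). Adding the 28-day tail (SAP 5.4.6): 144 + 4 = 148 weeks. A patient who stops at Week 96 has 96 + 4 = 100 weeks; one who stops at Week 48 has 52; one who stops at Week 24 has 28.

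**2. Crude percentage by window.** Assume a constant first-event rate r per year and 52.18 weeks per year. Expected incidence is 1 − exp(−r × weeks / 52.18). With r = 0.2, an illustrative value:

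- 52 weeks: 1 − exp(−0.2 × 0.997) = 18.1%
- 100 weeks: 1 − exp(−0.2 × 1.916) = 31.8%
- 148 weeks: 1 − exp(−0.2 × 2.836) = 43.3%

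**3. Two groups with the same true rate.** The exposure pattern is assumed, because the documents give none. In group A everyone is dosed for 144 weeks (window 148). In group B, 25% stop at Week 24 (window 28) and 75% at Week 96 (window 100). Group B's incidence is 0.25 × the 28-week value + 0.75 × the 100-week value. At r = 0.2 that is 0.25 × 10.2 + 0.75 × 31.8 = 26.4%.

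| r per year | A | B | Difference (points) |
|---|---|---|---|
| 0.10 | 24.7% | 14.4% | 10.3 |
| 0.20 | 43.3% | 26.4% | 16.9 |
| 0.25 | 50.8% | 31.7% | 19.1 |
| 0.50 | 75.8% | 52.1% | 23.7 |
| 1.00 | 94.1% | 74.3% | 19.8 |

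The whole difference comes from exposure.

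**4. Effect of each remedy in that example, r = 0.2.** Counting onset only through Week 96 gives A 30.8%, and B 0.25 × 10.2 + 0.75 × 30.8 = 25.6%. The gap falls from 16.9 to 5.2 points: the extension part goes, the early-exit part stays. Expected person-years at risk to first event are incidence / r: 0.433 / 0.2 = 2.165 per patient in A and 0.264 / 0.2 = 1.32 in B. Patients with a first event per patient-year is then 0.2 in both groups, and the gap vanishes.

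**5. Precision.** Exact 95% intervals: 10 of 20 gives 27.2% to 72.8%; 8 of 16 gives 24.7% to 75.3%; 2 of 4 gives 6.8% to 93.2%. The subgroup sizes are assumed, because the documents give no ambulatory counts.

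**The case against.** **No bias is shown.** A reader might infer that the ambulatory split is biased. The documents do not support that. They give no exposure, dropout or counts by ambulatory status, and what ends the extension is not tied to that status. The gaps in step 3 come from an assumed pattern. This stands, and limits the point to a risk that the plan leaves open.

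**No comparison is planned.** A reader might also infer that the tables test one ambulatory group against the other, or this study against another. The tables are only presented by status, the safety analyses are descriptive, and no between-group or cross-study AE contrast is visible. This stands too, but a descriptive percentage still needs a stated time at risk.

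**The Week 96 mismatch is narrow.** It would be too strong to say that the other safety tables stop at Week 96. Only the lab and ECG shift tables do. The summaries by time point and the markedly abnormal counts by visit have no stated cut.

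**Exposure is partly reported.** Days on drug are calculated, exposure is summarized, and AEs are listed. With about 20 patients a reader could trace onset and exposure one by one. That lowers the risk, but leaves the tables without a denominator in time.

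**Rates have faults of their own.** They are easy to interpret only under a roughly constant hazard. Events that cluster early, as infusion reactions may, would look rarer in patients followed longer. With so few patients the rates will also be unstable. Both points stand, and are why the crude percentages should stay.

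**The text is incomplete.** Parts of the SAP are not visible, so absence is judged on the visible text.

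**Conclusion.** The point holds. The planned AE percentages count patients correctly, but over a time at risk that can run from early exit to about 148 weeks, with no common horizon and no person-time denominator in the visible text.

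The size depends on assumptions. At a constant 0.2 events per year, the expected percentage more than doubles between a 52-week and a 148-week window (18.1% to 43.3%). Under the assumed exit pattern and rates of 0.1 to 1.0 per year, two groups with equal risk would differ by about 10 to 24 points. Neither the rates nor the exit pattern comes from the documents. A distorted ambulatory split is therefore possible, not demonstrated, and in groups this small random error may be as large.

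This is a change that should be made. It is not a flaw that invalidates the safety analysis.

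**What to change.** Keep the crude percentages and add three things to the SAP.

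1. **Fixed horizon.** A display of TEAEs with onset through Week 96, by ambulatory status and overall. State whether Week 96 means a fixed study day or the date of the visit.
2. **Exposure.** A summary of days on study drug and total patient-years, by ambulatory status and overall.
3. **Rates.** For overall TEAEs, treatment-related TEAEs, treatment-emergent SAEs and AESIs, the number of patients with a first event per patient-year at risk. Time at risk runs from first dose to first onset or, with no event, to last dose plus 28 days.

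Two rules need writing.

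- **Partial onset dates.** SAP 5.4.4 fills in a missing day only to calculate AE duration. Extend its first-of-month start-date rule to the rates, but never place onset before first dose. Add a rule for onsets with no known month.
- **SAEs.** SAP 5.5.7.1 tabulates SAEs whether or not they are treatment-emergent. The rate must use only treatment-emergent SAEs, so that numerator and person-time match.

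Say also how the 28-day tail is handled for patients who move to commercial drug or another study, since Protocol 8.5 requires no End of Study visit from them.

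**Cost.** A little more programming, from dose dates and AE onset dates already collected. No study procedure changes. The rates assume a roughly constant hazard and will be imprecise with about 20 patients; label them descriptive.

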5.5.7.1.1. Adverse Events of Special Interest

Summaries of TEAEs of special interest (AESIs) and other AEs of Interest will be summarized by SOC and PT. All SMQs listed below will include broad and narrow terms. The AESIs are:

- Hypersensitivity (Anaphylactic Reaction SMQ and Anaphylactic/Anaphylactoid Shock Conditions SMQ)
- Renal Toxicity (Acute Renal Failure SMQ)
- Leukopenia and Neutropenia (Haematopoietic SMQ)
- Infusion Site Reactions (Extravasation Events SMQ and the following PTs: Application Site Erythema, Application Site Rash, Catheter Site Haematoma, Catheter Site Haemorrhage, Catheter Site Related Reaction, Infusion Site Rash, Infusion Site Swelling)
- Severe Cutaneous Adverse Reactions (Severe Cutaneous Adverse Reactions SMQ)
- Infusion Related Reactions (PTs of Nausea, Vomiting, Pyrexia, Body
 Temperature Increased, Erythema, Flushing Infusion Related Reaction,
 Hypotension, Blood Pressure Decreased, Diastolic Hypotension, Orthostatic
 Hypotension, Procedural Hypotension, Blood Pressure Ambulatory Decreased,
 Blood Pressure Diastolic Decreased, Blood Pressure Orthostatic Decreased, Blood
 Pressure Systolic Decreased, Blood Pressure Systolic Inspiratory Decreased)
- Drug Induced Hepatotoxicities (Cholestasis and Jaundice of Hepatic Origin SMQ, Hepatic Failure, Fibrosis and Cirrhosis and Other Liver Damage-Related Conditions SMQ, Hepatitis, Non-infectious SMQ, Liver Neoplasms, Benign (incl Cysts and Polyps) SMQ, Liver Malignant Tumours SMQ, Liver Tumours of Unspecified Malignancy SMQ, Liver Related Investigations, Signs and Symptoms SMQ, Liver-Related Coagulation and Bleeding Disturbances SMQ)
- Cardiac Events (Cardiomyopathy SMQ, Cardiac Failure SMQ, and Arrhythmia Related Investigations, Signs and Symptoms SMQ)
- Coagulopathy (Haemorrhage Terms (excluding lab terms) SMQ, Haemotopoietic Thrombocytopenia SMQ, PTs in the Embolism and Thrombosis High Level Group Terms (HLGT)

The Other AEs of Interest are:

 Port-Related Events⁺ (Embolic and Thrombotic Events, Venous SMQ, Extravasation Events (Injections, Infusions and Implants) SMQ, PTs in the following High Level Terms (HLTs): Sepsis, Viraemia and Fungaemia NEC, Implant and Catheter Site Reactions, PTs in the following HLGTs: Endocardial Disorders and Device Issues. In addition, a search will be performed on the verbatim terms for "port", "central venous" and "central line")

- Fractures (PTs in the following HLGTs: Fractures and Bone and Joint Injuries)
- Falls (search of verbatim terms for "fall")
- + For subjects who have a port, Port-Related Events will only be identified after the port insertion occurred.

A corresponding listing will be generated for each table.

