5.3. Clinical Experience with Eteplirsen

Two Phase 1 clinical studies of eteplirsen have provided initial support and proof-of-concept for the safety and potential efficacy of eteplirsen in the treatment of DMD. In light of the positive findings from the two Phase 1 studies, a 28-week, double-blind, placebo-controlled Phase 2 study (Study 4658-us-201) was initiated to assess efficacy, safety, tolerability, and pharmacokinetics (PK) of eteplirsen. Twelve patients aged 7 to 13 years were randomized to receive once-weekly intravenous (IV) infusions of eteplirsen (30 or 50 mg/kg) for 28 weeks, or once-weekly placebo infusions for 24 weeks followed by eteplirsen infusion (30 or 50 mg/kg) for 4 weeks. At Week 28, these same 12 patients were enrolled in the extension study (Study 4658-us-202) where they continued open-label eteplirsen at the same dose they were receiving upon completion of the parent study.

Two other eteplirsen studies are ongoing (Study 4658-203, a Phase 2 study in patients 4 to 6 years of age; and Study 4658-301, a Phase 3 confirmatory safety and efficacy study).

Based on the cumulative available safety data from these studies, eteplirsen has been shown to be well tolerated, with low rates of serious or severe adverse events (AEs). The following common AEs are categorized as adverse drug reactions given their frequency relative to placebo: headache, arthralgia, vomiting, nausea, upper respiratory tract infection, nasopharyngitis, and cough. In addition, the following events are also categorized as adverse drug reactions given their temporal relationship to eteplirsen administration: erythema, flushing, and mild temperature elevation.

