11.3.1. Relationship to Investigational Product

For each AE, the Investigator determines whether there is a reasonable likelihood that the AE may have been caused by the study treatment according to the categories below:

Unrelated: The event is clearly not related to the IP

Possibly/probably related: The event could be related/is likely to be related to the IP

Definitely related: The event is clearly related to the IP

AEs that the Investigator or Sponsor considers to be possibly, probably, or definitely related to the IP will be considered adverse drug reactions.

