11.4. Recording Adverse Events

All AEs/SAEs experienced from the time of informed consent/assent to the last follow-up will be recorded within each patient's CRF. Information should include: a concise description of the event; date and time of event onset and resolution; determination of seriousness, severity, corrective treatment, outcome, and relationship to IP or study procedure or underlying disease; and any action taken will be recorded. Resolution occurs when the patient has returned to his baseline state of health or further improvement or worsening of the event is not expected.

Whenever possible, a diagnosis will be recorded as an AE, rather than symptoms or isolated laboratory abnormalities related to that diagnosis. Several symptoms or laboratory results that are related to the same diagnosis can thus be part of the same AE. A medical or surgical procedure is not an AE; rather the condition leading to the procedure should be recorded as the AE. Similarly, death is not an AE, but is rather the outcome of the AE(s) that resulted in death. If the AE(s) leading to death are not known, then death must be reported as an AE. All AEs will be followed until the resolution of AE, completion of the patient's study participation, or study termination, whichever occurs first. SAEs will be followed until resolution or until the condition stabilizes or returns to baseline status.

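### The Infusion Related Reactions AESI is defined by event terms alone, so its table cannot show whether events cluster around infusions

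*SAP*

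**What the plan says.** SAP 5.5.7.1.1 lists the AESIs and summarises each by system organ class and PT. The infusion category opens with "Infusion Related Reactions (PTs of Nausea, Vomiting, Pyrexia, Body" and is a list of terms only. A listing accompanies each AESI table; its columns are not specified.

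The only timing condition on this category is the treatment-emergent rule in SAP 5.4.6, which admits any event "on or after the initiation of the first dose of eteplirsen and within 28 days of last dose". SAP 5.5.7.1 adds the usual counting rule: "Multiple occurrences of the same AE (at the PT level) in the same subject will be counted only once".

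Protocol 11.4 requires the "date and time of event onset and resolution" for every adverse event. SAP 5.4.6 takes first and last dose dates from the study drug administration form, and SAP 5.5.5 lists dosing information.

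Protocol 5.3 explains how the known reactions were identified. Three were classed as reactions "given their temporal relationship to eteplirsen administration: erythema, flushing, and mild temperature elevation". Others were "categorized as adverse drug reactions given their frequency relative to placebo: headache, arthralgia, vomiting, nausea", among further terms.

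**The concern.** The category is named for a relation to the infusion, but membership does not depend on that relation. Under weekly dosing, the treatment-emergent period runs without a gap from the first dose to 28 days after the last. An isolated vomiting episode midway between two doses therefore meets the definition as fully as one that starts during an infusion.

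Safety and tolerability is the primary objective and there is no control group. The comparison with placebo that protocol 5.3 used for nausea and vomiting is not available within this study. Timing, which protocol 5.3 used for erythema, flushing and temperature elevation, is available, but the planned summary does not use it. A patient with one fever on treatment and a patient with fever after many infusions each count once in the pyrexia row, and neither the row nor any other visible table shows when the fevers began relative to dosing.

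**Working it through.** The documents give no figure for this point, so there is none to reproduce. The check has three parts.

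**1. What the term list contains.** Counted from SAP 5.5.7.1.1:
- nausea and vomiting: 2
- pyrexia and increased body temperature: 2
- erythema: 1
- flushing: 1
- Infusion Related Reaction: 1
- hypotension and decreased-blood-pressure terms: 10

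Total 2 + 2 + 1 + 1 + 1 + 10 = 17. The comma between Flushing and Infusion Related Reaction is missing in print; read literally, the count is 16. The other entries are general terms that can arise at any time, so membership alone says nothing about timing.

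**2. Which planned outputs use timing.** SAP 5.5.7.1 splits adverse events by organ class, PT, severity, relationship and baseline ambulatory status. SAP 5.5.7.1.1 tabulates AESIs by organ class and PT. None of these visible tables classifies onset by time from infusion. The same section does attach a timing rule to Port-Related Events, which count only after port insertion in patients who have a port. A timing condition on a category is therefore already within this SAP's framework.

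**3. How much of the period a window would cover.** Inputs: 96 weekly doses (protocol 9.2), infusion of 35 to 60 minutes (protocol 9.2), and 28 days after the last dose (SAP 5.4.6). No missed doses are assumed.
- Treatment-emergent period: 95 × 7 + 1 + 28 = 694 days.
- 24 hours per infusion: 96 × 1 = 96 days; 96/694 = 13.8%.
- Start of infusion to 24 hours after its end, 35-minute infusion: 96 × 24.58/24 = 98.3 days; 98.3/694 = 14.2%.
- The same, 60-minute infusion: 96 × 25/24 = 100 days; 100/694 = 14.4%.
- Infusion day plus next day: 96 × 2 = 192 days; 192/694 = 27.7%.
- Full 48-week extension: 144 doses, 143 × 7 + 1 + 28 = 1,030 days; 24 hours per infusion covers 144/1,030 = 14.0%.

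The 3-day dosing tolerance does not make these windows overlap, because protocol 9.2 bars two doses within 60 hours.

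Most of the period that qualifies an event for this AESI thus lies away from any infusion: about 86% under the 24-hour window, and 72.3% (100 − 27.7) under the two-day window.

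**The case against.** **A broad term search is a legitimate descriptive choice.** Almost every AESI in this section is a term or query search without a timing rule, PT names seldom encode timing, and counting once per PT applies to all adverse event tables. This stands. That only one term names the infusion is not in itself a defect. The point is narrower: the summary offers no view of timing for the one category whose name asserts it.

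**The information can be recovered.** Onset times are recorded, the AESI and dosing data are listed, and a reader needs to look up only one preceding infusion per episode. This stands as well, and it is why the point is modest. It does not put the result in a summary.

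**Other tables help.** The Infusion Related Reaction PT has its own row, but it holds only events coded that way. The treatment-related tables cover all treatment-emergent events and rest on an open-label judgement. Its middle category reads "The event could be related/is likely to be related to the IP", and "it is assumed that an AE without a relationship is treatment-related". Both help in part; neither shows timing.

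**Detection is not even over the week.** Protocol 9.2 has patients observed for at least an hour after each infusion. Protocol 10.3.2 takes vital signs 5, 30 and 60 minutes after, with a reduced schedule possible after the first year. Twelve of the 17 terms concern temperature or low blood pressure. Unrelated events are therefore more likely to be noticed near an infusion. This objection stands in full: a reader might take 14% or 27.7% as the share expected by chance and test against it, but the documents give no basis for assuming evenly spread detection.

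**Infusion clock times may not be held.** No passage states that they are recorded; SAP 5.4.6 mentions dose dates only. This stands and governs which window is feasible.

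**Conclusion.** The AESI has no onset condition beyond the treatment-emergent window, and no visible planned table separates onsets near an infusion from the rest. As planned, the summary cannot show clustering around infusions. That conclusion rests on the wording of the SAP sections in the text supplied, parts of which are redacted. The coverage figures assume 96 weekly doses with none missed; the window lengths are illustrative, since no document sets one.

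Three stronger readings are tempting and are not supported:
- A reader might infer that the SAP merges all these events into one inflated count. It tabulates by organ class and PT, and no pooled row is stated, so nausea, vomiting, erythema and flushing keep their own rows.
- A reader might infer how many patients would be wrongly labelled. The documents give no background rate for these terms, so no such number can be derived.
- A reader might infer that the study cannot assess infusion reactions, or that its conclusions are compromised. The data are collected and listed, the analyses are descriptive, and no decision rule depends on this table.

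What remains is a worthwhile, low-cost improvement to one summary.

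**What to change.** Keep the all-onset organ class and PT table as it is. In SAP 5.5.7.1.1:
- Add, for the same terms, the number of patients and of episodes with onset in a window that the sponsor pre-specifies before database lock. With dose dates alone this could be infusion day plus next day; if infusion clock times are held, start of infusion to 24 hours after its end. The choice is the sponsor's.
- Where the onset time is missing, count the episode as within the window, and show how many episodes were treated so.
- Add time since last infusion to the AESI listing.
- State beside the table that the window's share of follow-up is not an expected proportion under chance.

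The cost is one table block and one listing column, from onset data and dose dates already collected; the 24-hour version also needs infusion clock times. No event is lost. The downsides should be stated: window length is a judgement, delayed reactions appear only in the all-onset table, and both recall at weekly visits and monitoring after infusions pull detected onsets towards infusion days.
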